6.14. Safety Analyses

Safety analyses for this study will be provided in the following manner:

- The analysis of safety parameters during Part A wherein the comparison between baricitinib and placebo is of primary interest, informing risks to treatment that can be evaluated relative to the potential efficacy advantages shown over the same acute treatment time course. The baricitinib-placebo differences will be formally statistically compared, where applicable. Data collected up to the time of rescue (if applicable) will be used in these comparisons.
- Secondly, the summary analysis of safety parameters which includes data collected during Part B will be provided. No formal statistical comparisons are planned.
- Thirdly, summarization of safety parameters after inception of treatment with baricitinib, experienced from the moment of randomization, from the time of switching from treatment with placebo to baricitinib, or from the point of rescue to treatment with baricitinib will be provided. As these comparisons do not result from some form of randomization, no formal statistical comparisons will be performed. These summaries will include all qualifying data from Parts A and B.

Thus, safety results will generally be prepared according to 4 formats:

- Part A, Week 0 (Visit 2) to Week 12 (Visit 9) covering exposures to randomized treatments prior to the primary timepoint at Week 12,
- Part A, Week 0 (Visit 2) to Week 24 (Visit 11) covering all of Part A but with censoring for patients after the point of rescue,
- Parts A and B combined from Week 0 (Visit 2) to Week 52 (Visit 15) for patients randomized to baricitinib but with censoring after the point of rescue,

- Parts A and B combined from Week 0 (Visit 2) to Week 52 (Visit 15) for patients randomized to baricitinib and for patients who change treatment to baricitinib from placebo covering all exposure to baricitinib.

Safety topics that will be addressed include the following: AEs, clinical laboratory evaluations, vital signs and physical characteristics, safety in special groups and circumstances, including Adverse Events of Special Interest (AESI) (see Section 6.14.4), and study drug interruptions.

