- a Assayed/calculated by a sponsor-designated laboratory.
- b Unscheduled blood chemistry (including CPK), hematology, and urinalysis panels may be performed at the discretion of the investigator. If tests are done to evaluate laboratory results to resume study drug, samples must be assayed centrally.
- c Estimated glomerular filtration rate for serum creatinine calculated by the central laboratory using the Modification of Diet in Renal Disease isotope dilution mass spectrometry traceable method.
- d The calculated creatinine clearance will be determined by the central laboratory each time a serum creatinine sample is collected using the Cockcroft-Gault equation: Men: $([140 - \text{age}] \times [\text{weight in kg}]) / (72 \times [\text{serum creatinine in mg/dL}])$ or $([140 - \text{age}] \times [\text{weight in kg}]) / (0.814 \times [\text{serum creatinine in } \mu\text{mol/L}])$. Women: $(\text{above formula}) \times 0.85$.
- e Fasting laboratory values for glucose and lipids will be required at baseline, Week 12, Week 24, and Week 52. If a patient attends these visits in a nonfasting state, this will not be considered a protocol violation. These tests may be performed nonfasting at all other visits.
- f For all women of childbearing potential, a serum pregnancy test (central laboratory) will be performed at Visit 1 and both urine (local laboratory) and serum pregnancy (central laboratory) tests will be performed at Visit 2 to determine study eligibility. Urine pregnancy tests (local laboratory) will also be performed at each subsequent study visit per study schedule.
- g To confirm postmenopausal status for women ≥ 40 and < 60 years of age, an FSH test will be performed. Nonchildbearing potential is defined as an FSH ≥ 40 mIU/mL and a cessation of menses for at least 12 months.
- h A positive hepatitis C antibody result will be confirmed with a positive hepatitis C virus result.
- i Microscopic examination of sediment will be performed only if abnormalities are noted on the routine urinalysis.
- j Test will be required at Visit 1 only to determine eligibility of patient for the study. In countries where the QuantiFERON-TB Gold or T-SPOT.TB test is available and, in the judgment of the investigator, medically preferred as an alternative to the PPD test for the evaluation of mycobacterium tuberculosis (MTB) infection, it may be used instead of the PPD test (positive tests excluded) and may be read locally.

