In addition to the LS means for each group, the within-group p-value, the standard deviation, minimum, median, and maximum will be displayed for continuous safety variables.

Data collected at early termination visits will be mapped to the next scheduled visit number for that patient.

The following is a description of the analysis groups planned for this study. Refer to Section 6.1.3 for the definitions of analysis populations used for the efficacy and safety analyses.

Analysis Groups for the Efficacy and Health Outcomes Data

Summaries of efficacy and health outcomes data for the Week 0 to Week 12 period, the Week 0 to Week 24 period with data up to rescue, and the Week 0 to Week 52 period with data up to rescue/switch will be presented according to the following treatment groups:

- Placebo: patients randomized to placebo excluding data obtained after the receipt of baricitinib 4 mg, either as rescue therapy or according to the protocol-designated switch to baricitinib 4 mg,
- Baricitinib 4 mg: patients randomized to baricitinib 4 mg excluding data obtained after the receipt of rescue therapy.

Summaries of efficacy and health outcomes data for patients who are rescued/switched will be presented according to the following treatment groups:

- Placebo (rescued): patients randomized to placebo who were rescued on or before Week 24,
- Placebo (switched, not rescued): patients switched to baricitinib from placebo at Week 24 and not rescued after the initiation of baricitinib,
- Placebo (switched, rescued): patients switched to baricitinib from placebo at Week 24 and rescued after initiation of baricitinib,
- Baricitinib (rescued): patients randomized to baricitinib who were rescued.

Analysis Groups for the Safety Data

Summaries of safety data for the Week 0 to Week 12 period and the Week 0 to Week 24 period with data up to rescue will be presented according to the following treatment groups:

- Baricitinib 4 mg: patients randomized to baricitinib excluding data obtained after the receipt of rescue therapy,
- Placebo: patients randomized to placebo using data obtained prior to the receipt of baricitinib as rescue therapy.

Summaries of safety data for the Week 0 to Week 52 period with data up to rescue/switch will be presented for baricitinib 4 mg for patients who were randomized to baricitinib excluding data obtained after receipt of rescue therapy.

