Further, for some AEs of interest, duration of the TEAE may be summarized or listed within patient AE listings. The duration of each event will be defined as the end date of AE minus the start date of treatment-emergence of the AE plus 1 day. If an AE has not ended by the date of study drug discontinuation, early discontinuation of the study/period, or completion of the study, it will be censored as of that appropriate final date.

In general, summaries of TEAEs, SAEs, AEs that lead to discontinuation from the study, and AEs that lead to temporary interruption or permanent discontinuation of study drug will include the number of patients in the safety population (N), frequency of patients experiencing the event (n), and percent of patients experiencing the event ($n/N \times 100$), and the exposure-adjusted incidence rate (EAIR). The EAIR will be expressed as the number of patients experiencing an

AE (n) per 100 patient years of exposure to treatment and is derived as 100 times the number of patients with the event divided by the sum of all patient exposure times (in years) to the treatment for the study/period. For any events that are gender-specific based on the displayed PT, the denominator used to compute the percentage will only include patients from the given gender. Treatment comparisons between treatment groups will be made using the Fisher exact test.

In an overview table, the number and percentage of patients in the safety population who experienced a death, a serious adverse event (SAE) (International Conference on Harmonisation [ICH]-defined, protocol-defined, and ICH- or protocol-defined), discontinuation from the study due to an AE or death, permanent discontinuation from study drug due to an AE or death, temporary interruption from study drug due to an AE, temporary interruption of study drug due to a lab abnormality, a TEAE, a TEAE rated as severe, or an AE possibly related to study drug based on the opinion of the investigator will be summarized by treatment.

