Change from the minimum value during the baseline period to the minimum value during the treatment period for selected laboratory tests will be summarized for patients who have both baseline and at least 1 post-baseline result. Baseline will be the minimum of non-missing observations in the baseline period. The minimum value in the treatment period will be used for this analysis. Similarly, change from the maximum value during the baseline period to the maximum value during the treatment period for selected laboratory tests will be summarized for patients who have both baseline and at least 1 post-baseline result. Baseline will be the maximum of non-missing observations in the baseline period. The maximum value in the treatment period will be used for this analysis. Original-scale data will be analyzed. Scheduled and unscheduled measurements will be included.

The change from baseline in laboratory assessments, using each of the 3 approaches above, will be summarized using standard descriptive statistics.

In addition, laboratory assessments will be summarized with descriptive statistics (n, mean, SD, minimum, median, and maximum) by time point. Summaries will be provided for baseline and for each postbaseline visit by treatment group, including change from baseline and percent change from baseline. These summaries will be based on patients who have both baseline and at least 1 postbaseline assessment.

The number and percent of patients with treatment-emergent abnormal, high, or low laboratory results at any time will be summarized by treatment group.

- A treatment-emergent **abnormal** result is defined as a change from normal at all baseline visits to abnormal at any time during the treatment period.
- A treatment-emergent **high** result is defined as a change from a value less than or equal to the high limit at all baseline visits to a value greater than the high limit at any time during the treatment period.
- A treatment-emergent **low** result is defined as a change from a value greater than or equal to the low limit at all baseline visits to a value less than the low limit at any time during the treatment period.

Scheduled and unscheduled measurements will be included in analysis of treatment-emergent abnormal, high, or low laboratory results. Differences between treatments (when appropriate) in incidence of treatment-emergent abnormal, high, or low laboratory results will be assessed using the Fisher exact test.

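### If placebo patients are rescued more often, the Week 0-24 safety tests compare crude percentages over unequal observation time and modestly overstate baricitinib's relative harm

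*SAP*

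**What the plan says.** SAP 6.14 makes the Part A baricitinib-placebo contrast the safety comparison of primary interest, to be formally tested where applicable: "Data collected up to the time of rescue (if applicable) will be used in these comparisons". The Week 0-24 format is described as "covering all of Part A but with censoring for patients after the point of rescue".

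SAP 6.1 cuts both arms at rescue. The placebo group is "patients randomized to placebo using data obtained prior to the receipt of baricitinib as rescue therapy"; the baricitinib group is "patients randomized to baricitinib excluding data obtained after the receipt of rescue therapy".

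The tests are on counts of patients:
- Adverse events (SAP 6.14.1): "Treatment comparisons between treatment groups will be made using the Fisher exact test".
- Laboratory results at any time (SAP 6.14.3): "Differences between treatments (when appropriate) in incidence of treatment-emergent abnormal, high, or low laboratory results will be assessed using the Fisher exact test".

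SAP 6.14.1 also shows an exposure-adjusted incidence rate (EAIR) beside the adverse event percentages. It divides patients with the event by all exposure in the period, and no test or interval is attached to it. SAP 6.14.3 specifies no such rate for laboratory abnormalities.

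Rescue begins at Week 16 for patients lacking 20% improvement in tender and swollen joint counts at both Week 14 and Week 16, and is at the investigator's discretion afterwards (SAP 5.3.3). A separate Week 0-12 safety format is planned.

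**The concern.** A patient rescued at Week 16 stays in the denominator of a 24-week percentage but can contribute an event during only 16 of the 24 weeks. Fisher's test treats that patient like one observed throughout. Because rescue follows nonresponse, an effective drug would leave placebo with more rescued patients and less follow-up. Even with identical true hazards, the crude percentages would then lean towards more harm on baricitinib, by an amount that depends on efficacy rather than safety.

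The loss differs by measure. By the study schedule (Protocol Attachment 1), hematology and chemistry have 9 postbaseline Part A visits (Weeks 1, 2, 4, 8, 12, 14, 16, 20, 24), and 7 fall by Week 16. Lipids, iron studies and QIDS-SR16 have two, Weeks 12 and 24. For lipids, Attachment 2 adds: "Fasting laboratory values for glucose and lipids will be required at baseline, Week 12, Week 24, and Week 52". A Week 16 rescue therefore removes half of those scheduled assessments.

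At stake is the meaning of the Week 0-24 p-values, which mix any real difference in harm with a difference in observation time.

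**Working it through.** **Inputs from the documents.** 144 patients per arm; ACR20 at Week 12 of 60% v 35% (SAP 5.2); earliest rescue at Week 16 (SAP 5.3.3); 24-week comparison cut at rescue (SAP 6.14).

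**Assumptions, not in the documents.** Rescue shares; all rescue at Week 16; the same constant event hazard in both arms; no other dropout; a 30% true 24-week risk for adverse events.

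**1. The plan's own figure.** Power for 60% v 35% by the normal approximation: z = [0.25 × √144 − 1.96 × √(2 × 0.475 × 0.525)] / √(0.60 × 0.40 + 0.35 × 0.65) = (3 − 1.384) / 0.684 = 2.36, so power is 99.1%. The stated 99% is reproduced. It is the only design figure available, and it says nothing direct about rescue.

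**2. Risk by Week 16.** With 24-week risk R = 0.30, the 16-week risk is 1 − (1 − R)^(16/24) = 1 − 0.70^(2/3) = 0.2116.

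**3. Crude risk in an arm with rescue share r.** (1 − r) × 0.30 + r × 0.2116. Mean observation is 24 − 8r weeks. The last column is the exact probability that Fisher's test at 144 per arm falsely shows more events on baricitinib; with no rescue it is 1.9%.

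| Rescue, placebo / baricitinib | Mean weeks | Crude % | Ratio | False signal |
|---|---|---|---|---|
| 10% / 5% | 23.2 / 23.6 | 29.1 / 29.6 | 1.02 | 2.3% |
| 20% / 7% | 22.4 / 23.4 | 28.2 / 29.4 | 1.04 | 3.1% |
| 30% / 10% | 21.6 / 23.2 | 27.3 / 29.1 | 1.06 | 4.0% |
| 45% / 15% | 20.4 / 22.8 | 26.0 / 28.7 | 1.10 | 5.7% |

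**4. Does an exposure-based rate remove it?** With the SAP's EAIR, the ratio at 45% / 15% is (28.67 / 22.8) / (26.02 / 20.4) = 0.986; across the four rows it runs from 0.986 to 0.998. The small overshoot comes from counting exposure after the first event. With time to first event or rescue as the denominator, the ratio is 1.00 by construction under a constant hazard.

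**5. Lipids, upper-range illustration.** Assume a 20% risk spread over two independent, equal-risk draws. One draw carries 1 − √0.80 = 0.1056. Crude risk is (1 − r) × 0.20 + r × 0.1056, giving ratios of 1.07, 1.11 and 1.18 at 20/7, 30/10 and 45/15. Repeat lipid values within a patient are unlikely to be independent. If 75% of ever-high patients are already high at Week 12 (an assumption), each rescue loses 0.25 × 0.20 = 0.05, and the 45/15 ratio is (0.20 − 0.15 × 0.05) / (0.20 − 0.45 × 0.05) = 0.1925 / 0.1775 = 1.08. At 90% it is 0.197 / 0.191 = 1.03.

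**6. A person-time rate does not fully repair lipids.** A Week 16 rescue removes one third of the time but half of the draws. On the independent-draw model, with time to first event or rescue as the denominator, the rate ratio is still 1.06 at 45/15 and 1.04 at 30/10.

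**The case against.** **Direction and size are conditional.** A reader might infer that the Week 0-24 tables will make baricitinib harms look larger than they are. The documents do not support that as fact: they give no rescue rates. Discontinuation for adverse events or laboratory criteria, which the calculation ignores, could shorten baricitinib follow-up and offset the effect. This stands.

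**The effect is small.** At 30/10 the gap is 1.8 percentage points. The 95% interval for the difference has half-width 1.96 × √(0.273 × 0.727/144 + 0.291 × 0.709/144), or about 10.4 points. No stated decision hangs on these p-values, and the error would overstate harm rather than hide it. This also stands and limits the priority.

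**Safeguards exist.** The Week 0-12 format ends before rescue, and the EAIR sits beside the adverse event percentages. Both help a careful reader. Neither changes the Week 0-24 p-values or covers the laboratory tables.

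**ACR20 nonresponse is not a rescue rate.** A reader might take 65% and 40% as rescue shares. Rescue depends on joint counts alone at Weeks 14 and 16. ACR20 nonresponse also includes patients who meet both joint criteria but fail the other components, and dropouts imputed as nonresponders.

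**Fisher's test is not named for everything.** A reader might suppose that QIDS-SR16 is tested by Fisher. SAP 6.14.4.11 plans ANCOVA, and a likelihood-ratio chi-square test for the shift summaries. For the lipid categories SAP 6.14.4.3 specifies tabulation and names only a likelihood-ratio test for shifts. Cumulative comparisons on crude percentages remain open to the same imbalance whichever test is used.

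**Conclusion.** The concern holds in conditional form. If placebo is rescued more often, the Week 0-24 Fisher comparisons observe placebo for less time and modestly overstate baricitinib's relative harm. For a 30% adverse event risk the false ratio is about 1.04 to 1.10 at assumed rescue of 20/7% to 45/15%, and negligible at 10/5%. This rests on equal constant hazards, all rescue at Week 16 and no other dropout. Events clustered early would shrink the effect; late ones would enlarge it. The lipid ratios of up to 1.18 are an upper-range illustration that depends on independent draws.

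The planned EAIR (adverse events only, all-exposure denominator, no test or interval) and the Week 0-12 format leave the Week 0-24 p-values uncorrected. This is a worthwhile, inexpensive improvement to make before unblinding, not a flaw that invalidates the safety analysis.

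One textual point affects the safeguard itself. SAP 6.14 labels Week 12 as Visit 9, whereas the schedule has Week 12 as Visit 7 and Visit 9 as Week 16. As written, the end of that window is ambiguous.

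**What to change.** In SAP 6.14:

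1. Add a Week 0 to Week 16 format using pre-rescue data, and place the formal Fisher tests for adverse events and for hematology and chemistry abnormalities there. No patient can be rescued earlier, so both arms have the same planned window and visits.
2. For Week 0-24, replace the Fisher p-value with an exposure-adjusted rate ratio or difference and its 95% confidence interval, with time to first event or rescue as the denominator. Give the same rates for treatment-emergent hematology and chemistry abnormalities.
3. For lipids, iron studies and QIDS-SR16, make the Week 12 assessment the tested between-arm comparison. A Week 0-16 table would use the same scheduled Week 12 assessment, and a rate does not fully correct for the lost one. Present cumulative Week 0-24 categories descriptively, with the number assessed at each visit.
4. Reconcile the Visit 9 label for Week 12 with the study schedule.

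The cost is SAP wording and one extra set of tables; no new data are needed. Events in Weeks 16-24 would no longer be formally tested on crude percentages, and the rate comparison assumes a roughly constant hazard.

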6.14.1. Adverse Events

Adverse events are recorded in the eCRFs. Each AE will be coded to system organ class (SOC) and preferred term (PT) using the MedDRA version that is current at the time of each database lock. Severity of AEs is recorded as mild, moderate, or severe.

A treatment-emergent adverse event (TEAE) is defined as an event that either first occurred or worsened in severity after the first dose of study treatment and on or prior to the date of the last visit within the treatment period being analyzed. Adverse events are classified based upon the MedDRA PT. The MedDRA Lowest Level Term (LLT) will be used in defining which events are treatment-emergent. The maximum severity for each LLT during the baseline period until the first dose of the study medication will be used as baseline. The treatment period (Parts A and B) will be included as postbaseline for the analysis. If an event is pre-existing during the baseline period but it has missing severity, and the event persists or reoccurs during the treatment period, then the baseline severity will be considered mild for determining any postbaseline treatment-emergence (ie, the event is treatment-emergent unless the severity is coded as mild postbaseline). If an event occurring postbaseline has a missing severity rating, then the event is considered treatment-emergent. Should there be insufficient data for AE start date to make this comparison (for example, the AE start year is the same as the treatment start year, but the AE start month and day are missing), the AE will be considered treatment-emergent. For events occurring on the day of the first dose of study treatment, a case report form (CRF) will be used to document whether the onset of the event was pre-treatment versus post-treatment in order to derive treatment-emergence.

For patients who were randomized to placebo and required rescue therapy or who were switched to baricitinib at the end of Part A, the AE severity just prior to rescue or switch to baricitinib will be used as baseline for assessing TEAE during baricitinib treatment.

Further, for some AEs of interest, duration of the TEAE may be summarized or listed within patient AE listings. The duration of each event will be defined as the end date of AE minus the start date of treatment-emergence of the AE plus 1 day. If an AE has not ended by the date of study drug discontinuation, early discontinuation of the study/period, or completion of the study, it will be censored as of that appropriate final date.

In general, summaries of TEAEs, SAEs, AEs that lead to discontinuation from the study, and AEs that lead to temporary interruption or permanent discontinuation of study drug will include the number of patients in the safety population (N), frequency of patients experiencing the event (n), and percent of patients experiencing the event ($n/N \times 100$), and the exposure-adjusted incidence rate (EAIR). The EAIR will be expressed as the number of patients experiencing an

AE (n) per 100 patient years of exposure to treatment and is derived as 100 times the number of patients with the event divided by the sum of all patient exposure times (in years) to the treatment for the study/period. For any events that are gender-specific based on the displayed PT, the denominator used to compute the percentage will only include patients from the given gender. Treatment comparisons between treatment groups will be made using the Fisher exact test.

In an overview table, the number and percentage of patients in the safety population who experienced a death, a serious adverse event (SAE) (International Conference on Harmonisation [ICH]-defined, protocol-defined, and ICH- or protocol-defined), discontinuation from the study due to an AE or death, permanent discontinuation from study drug due to an AE or death, temporary interruption from study drug due to an AE, temporary interruption of study drug due to a lab abnormality, a TEAE, a TEAE rated as severe, or an AE possibly related to study drug based on the opinion of the investigator will be summarized by treatment.

The number and percent of patients with TEAEs will be summarized by treatment group using MedDRA PT nested within SOC. The SOCs will be ordered alphabetically, and events will be ordered within each SOC by decreasing frequency in the baricitinib group (or combined baricitinib group, as appropriate). As additional tables, the number and percent of patients with TEAEs will be summarized by treatment using MedDRA PT (without regard to SOC) and the number and percent of patients with TEAEs will be summarized by treatment using only the MedDRA SOC. Events will be ordered by decreasing frequency in the baricitinib group.

The number and percent of patients with TEAEs will be summarized by maximum severity by treatment using MedDRA PT nested within SOC for all TEAEs. For each patient and TEAE, the maximum severity for the MedDRA level being displayed (PT and SOC) is the maximum postbaseline severity observed from all associated LLTs mapping to that MedDRA level. For the "Severe" category, comparisons between treatment groups will be made using the Fisher exact test for each PT and SOC.

Adverse events considered possibly related to study drug by the investigator will be summarized by treatment group using MedDRA PT nested within SOC. A possibly-related event is defined as an event recorded on the eCRF as "Yes" to the question "Is the event possibly related to study drug?" Events will be ordered by decreasing frequency in the baricitinib group (or combined baricitinib group, where appropriate), within alphabetical SOC. If the investigator's determination of possible relationship to study drug is missing, then the event will be considered as "related".

Follow-up emergent adverse events (FEAEs) will be established for the post-treatment follow-up Period. An FEAE is an event that either first occurred or worsened in severity after the last visit during the treatment period. The baseline severity for FEAE is the severity level at the last visit from the treatment period; otherwise, FEAE processing is similar to TEAE processing. Follow-up AEs will be summarized in a similar manner as TEAEs (using MedDRA PT within SOC) according to groups defined by the treatment the patients were receiving prior to entering the follow-up period.

An individual listing of all AEs including preexisting conditions will be provided. A separate listing will include all AEs that led to discontinuation from the study.

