6.10. Treatment Exposure

Duration of exposure to each study drug will be summarized for the safety population using descriptive statistics (n, mean, SD, minimum, median, maximum). Cumulative exposure and duration of exposure will be summarized in terms of frequency counts and percentages by category and treatment group.

Overall exposure will be summarized in total patient-years which are calculated according to the following:

Exposure in patient-years = sum of duration of exposure in days (for all patients in treatment group) / 365.25.

The summary for the first database lock (end of Part A) will include exposure to each treatment plus exposure for the subset of patients who are rescued during Part A from each randomized therapy.

The summary for the final lock (end of Parts A and B) will include all exposures for patients randomized to baricitinib and placebo, plus all exposures subsequent to rescue or switch to baricitinib. For the baricitinib treatment group, exposure will be calculated including the subset of patients who are rescued.

Duration of exposure will be calculated as follows:

1. Baricitinib group:

- Duration of exposure to baricitinib excluding exposure after the initiation of rescue therapy will be calculated as: [date of last study drug treatment prior to rescue – date of first study drug dose (Visit 2) + 1].
- Duration of exposure to baricitinib after the initiation of rescue therapy will be calculated as: (date of last study drug treatment – date of first baricitinib dose as rescue therapy + 1).

2. Placebo group:

- Duration of exposure to placebo excluding exposure after the initiation of rescue therapy will be calculated as: [date of last study drug treatment prior to rescue – date of first study drug dose (Visit 2) + 1].
- Duration of exposure to baricitinib after the initiation of rescue therapy will be calculated as: [date of last study drug treatment – date of first baricitinib dose as rescue therapy + 1].
- Duration of exposure to baricitinib after switch will be calculated as: (date of last study drug treatment (before rescue, if applicable) – date of first dose of study drug after switch + 1).

Summaries of treatment exposure will also include all baricitinib exposures.

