6.14.1.1. Common Adverse Events

The number and percent of patients with TEAEs, including the EAIR, will be summarized by treatment group using MedDRA PT nested within SOC for common TEAEs (ie, TEAEs that occurred in $\geq 2\%$ (before rounding) of any treatment group. Events will be ordered by decreasing frequency in the baricitinib group (or combined baricitinib group, where appropriate) within alphabetical SOC.

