6.14.4.8. Malignancies

Malignancies will be identified using terms from the malignant tumours SMQ (SMQ 20000194).

A by-patient listing for all patients having a malignancy event at any time will be provided and will include the information whether or not the event is considered as SAE, its relatedness to study drug, and whether or not it led to discontinuation from the study, led to permanent study drug discontinuation, or led to temporary study drug interruption.

If the number of events in the study warrants a table summary, the number and percent of patients with TEAEs associated with malignant tumors will be summarized by treatment group using MedDRA PT. Events will be ordered by decreasing frequency in the baricitinib group (or combined baricitinib group, where appropriate). Additional summaries will give an overview of malignancies. First, the total number of patients with malignant tumors which are SAEs by ICH GCP or by protocol, by ICH GCP, and by protocol only, will be provided. Second, the number of patients with TEAEs associated with malignant tumors that were rated as severe, and that were considered related to study drug in the opinion of the investigator, will be provided. Third, the number of patients with TEAEs associated with malignant tumors that led to discontinuation from the study, that led to permanent study drug discontinuation, and that led to temporary study drug interruption will be provided. EAIR will also be calculated for each PT. Tumors that are gender-specific, based on PT, will have the denominators limited to patients of that gender. Treatment comparisons may be made using the Fisher exact test.

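### The exposure-adjusted incidence rate keeps counting exposure after the first event, so it understates first-event rates for frequent adverse events and falls as the window lengthens

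*SAP*

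**What the plan says.** SAP 6.14.1 (Adverse Events) defines the EAIR per 100 patient-years of exposure. It is "derived as 100 times the number of patients with the event" and this count is "divided by the sum of all patient exposure times (in years) to the treatment for the study/period".

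SAP 6.10 (Treatment Exposure) supplies the denominator: "Exposure in patient-years = sum of duration of exposure in days (for all patients in treatment group) / 365.25". A patient's exposure runs from first dose to last dose or, where data are cut at rescue, to the "date of last study drug treatment prior to rescue". The onset date of an adverse event does not enter. The censoring described in 6.14.1 concerns how long an event lasted, and the censoring in 6.14 is at rescue. Neither stops person-time at a first event.

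The EAIR has a general role, set by the sentence in 6.14.1 that begins "In general, summaries of TEAEs, SAEs, AEs that lead to discontinuation from the study". It is named again for common events in 6.14.1.1 ("The number and percent of patients with TEAEs, including the EAIR, will be summarized by treatment group") and for malignancies in 6.14.4.8 ("EAIR will also be calculated for each PT"). The between-arm comparison does not use it: "Treatment comparisons between treatment groups will be made using the Fisher exact test".

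**The concern.** A first-event incidence rate divides patients with a first event by time at risk of a first event. Here a patient who has had the event can add nothing more to the numerator but goes on adding to the denominator until the last dose. The result is lower than the first-event rate, and the gap grows with the proportion of patients affected and with how early the event occurs.

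Two uses are at stake. The first is the level of the rate for frequent events, such as a common preferred term, and for any system organ class or all-infection total to which the general rule is applied. The second is comparison between windows. The SAP reports safety over Weeks 0 to 12, 0 to 24 and 0 to 52, and pools all baricitinib exposure whatever its length. A per-patient-year figure invites the reader to set these side by side, and this one drifts downwards as follow-up lengthens even if the hazard never changes.

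**Working it through.** **Inputs.** The formula is from SAP 6.14.1 and 6.10, and the windows from SAP 6.14. The documents state no EAIR and no adverse-event risk, so there is no figure of the plan's own to reproduce. All risks below are assumptions, shown as a range.

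**Step 1: the two rates.** Let r be the proportion with the event over a window of T years. Assume everyone has full exposure and the hazard is constant.
- SAP form: 100 × r / T
- First-event form: 100 × [−ln(1 − r)] / T
- Understatement: 1 − r / [−ln(1 − r)]. T cancels, so for a given r it does not depend on window length.

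**Step 2: Weeks 0 to 24.** T = 168 / 365.25 = 0.460 years.

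| Assumed risk | SAP form, per 100 PY | First-event form, per 100 PY | Understatement |
|---|---|---|---|
| 2% | 4.3 | 4.4 | 1.0% |
| 5% | 10.9 | 11.2 | 2.5% |
| 10% | 21.7 | 22.9 | 5.1% |
| 20% | 43.5 | 48.5 | 10.4% |
| 40% | 87.0 | 111.1 | 21.7% |

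Example at 20%: −ln(0.8) = 0.2231; 0.2231 / 0.460 gives 48.5; 0.20 / 0.460 gives 43.5; 1 − 0.20 / 0.2231 = 10.4%.

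**Step 3: same hazard, longer window.** For 52 weeks, T = 364 / 365.25 = 0.997 years. The 52-week risk is 1 − (1 − r)^(52/24).
- 20% at Week 24: 52-week risk 1 − 0.8^2.167 = 0.383; SAP form 38.3 / 0.997 = about 38, against 43.5 at Week 24, an apparent fall of about 12%.
- 40% at Week 24: 52-week risk 0.669; SAP form about 67, against 87.0, an apparent fall of about 23%.
- 5% at Week 24: 52-week risk 0.105; SAP form 10.6, against 10.9, a fall of about 3%.

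The first-event form stays at 48.5, 111.1 and 11.2 respectively.

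**Step 4: dependence on onset.** With equal exposure, and first events occurring on average at a fraction g of the exposure period, the understatement is r × (1 − g). At r = 20% it is 10% for g = 0.5 and 15% for g = 0.25, so earlier onset widens the gap. For an event that ends treatment there is almost no exposure afterwards, and the two denominators nearly coincide.

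**Step 5: unequal exposure from rescue.** Assume 40% of placebo and 10% of baricitinib patients leave the Week 0 to 24 window at Week 16. With no true difference in hazard, the ratio of the two SAP-form rates is 0.998, 0.991 and 0.981 at full 24-week risks of 5%, 20% and 40%. The present EAIR therefore handles unequal rescue almost as well as the first-event rate does.

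**The case against.** The strongest reply is that the SAP says plainly what it computes: patients with the event per 100 patient-years of exposure. Sections 6.14.1 and 6.10 agree, and nothing promises a first-event hazard. That stands. This is a choice of estimator, not a contradiction. But the figure is called an incidence rate, and no other section repairs the denominator.

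Second, the effect is small where the SAP names the EAIR for specific displays, which are by preferred term. At risks of 2 to 5% the shortfall is 1 to 2.5%. That stands too, and limits the point to frequent terms and groupings.

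Third, a reader might infer that comparisons between arms are distorted. For instance, a hazard ratio of 1.5 with 40% risk on placebo would appear as 1.34 when one EAIR is divided by the other. The documents do not support that as a fault. No EAIR ratio, interval or test is planned, and with equal exposure the quotient is simply the risk ratio, which is a valid measure.

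Fourth, a reader might take a high overall event rate, say 60% with any event, and cite a 35% understatement. The documents give no such risk, and the overview table in 6.14.1 lists only numbers and percentages. The figure would apply only if the general EAIR rule were extended to totals.

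Finally, stopping at the first event makes windows comparable only if the hazard is roughly constant. If events cluster early, first-event rates also fall with follow-up, but that change would then reflect the data rather than the formula.

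**Conclusion.** The point holds in a limited form and is a cheap improvement. The EAIR understates the first-event incidence rate, by about 1 to 2.5% at risks of 2 to 5%, 5% at 10%, 10% at 20% and 22% at 40%, and hardly at all for events leading to permanent discontinuation. These sizes rest on assumed risks, a constant hazard and full exposure. Earlier onset would make them larger.

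The practical consequence is that Week 24 EAIRs should not be read beside Week 52 or all-baricitinib EAIRs for frequent events: at a constant hazard, a 20% Week 24 risk shows as 43.5 and then about 38 per 100 patient-years. Percentages, Fisher p-values and every planned test are unaffected.

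**What to change.** In SAP 6.14.1, redefine the rate for each displayed term as 100 × patients with the event / patient-years at risk. Stop a patient's exposure at the first event for that term, or otherwise at the end of exposure for the period. Report it by treatment and period with a 95% CI. Keep the present figure as a secondary display, labelled as patients per 100 patient-years of total exposure.

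Event onset and dosing dates are already collected, so no new data, visits or tests are needed. The cost is SAP wording, a code change and a separate person-time denominator for each term. Reported rates will rise, slightly for rare events and noticeably for common groupings.
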